8.3 Secondary objectives and outcome measures

Objective	Outcome measure	Time point(s) of evaluation of this outcome measure (if applicable)
1. To compare the effect on HRQoL of both treatment arms	HRQoL using standard, validated patient-reported outcome measures (PROMs) questionnaires: IPSS, EQ-5D-5L, EPIC and MAX- PC (Modified 18 item)	Baseline, 6wks post- treatment and 3mths, 6mths, 12mths post-randomisation, thereafter every 12 months until the end of the study.
2.To compare the effect on health care resource	Health care resource utilisation and cost-effectiveness in terms	Baseline, 3mths, 6mths, 12mths post-randomisation,

		· · · · · · · · · · · · · · · · · · ·
utilisation of both treatment arms	of cost per quality-adjusted life year (QALY)	thereafter every 12 months until the end of the study.
3.To compare the short and medium term serious adverse events related to treatments in both treatment arms	Short, medium and long-term serious adverse events related to treatments	Short term: 31 days Medium term: 3 years
4.To determine the proportion of patients needing repeat partial ablation treatment	Proportion of patients needing repeat PA treatment in the PA group	Documentation of the need for repeat PA treatment in the PA group – at 1 year post- treatment and 3 years post- treatment (for those that reach this time point in the study's lifetime)
5.To evaluate the accuracy of current mpMRI imaging and biopsy protocols in determining suitability of patients for PA	The proportion of prostatectomy patients who develop high-risk disease or bilateral intermediate disease	After histopathological evaluation (only in men who have had RP, including salvage RP)
6.To determine disease progression beyond the prostate, including local spread and development of metastases	Time to disease progression (including local and distal recurrence)	At a minimum 12 months post-randomisation follow-up of the last recruited participant, but will be longer for those recruited early in the study.
7.To determine medium-term disease-specific and overall mortality	Time to disease-specific and overall mortality	At a minimum 12 months post-randomisation follow-up of the last recruited participant, but will be longer for those recruited early in the study.

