9.2 Collection of outcome data and follow-up assessments

Participants will undergo research specific visits and receive communications from the PART study team to collect outcome data.

Participants will subsequently be followed up in clinic approximately **six weeks post-operatively** and **three-monthly** post-treatment in the first year, and then approximately every **6 months** as per routine NHS care for up to 5 years post-randomisation depending upon when they are recruited into the study. If, at any point, disease progression is suspected, the patient will be re-staged as per NHS standard care.

Participants receiving PA will be required to attend in-person follow-up clinic visits for mpMRI at 1 week, 6 months, 12 months and 36 months[#] post- treatment and for prostate biopsies at 12 months and 36 months[#] (targeted and/or systematic, depending on mpMRI result).

Participants will be sent HRQoL questionnaires (PORPUS, IPSS, EPIC, EQ-5D-5L, and MAX-PC (modified 18 item)), and health care use questionnaires to complete electronically (a postal option will also be made available where required) at 6 weeks post-treatment and at 3 months, 6 months, 12 months, 24 months[#] and 36 months[#] post- randomisation.

Treatment complications and unexpected serious adverse events related to the study intervention will be collected using a combination of medical notes review, Health Care Use Questionnaire review and asking patients at follow-up appointments, and/or when a member of the research team becomes aware that a serious adverse event has occurred.

For participants who have undergone treatment using PA, additional imaging and repeat biopsies could also be triggered by a rise in PSA of at least 50% over a period of 12 months, or due to clinical concern.

Refer to section 16 for full details of outcome data collection and follow-up assessments.

[#]24-month and 36-month follow-up of all 800 participants is subject to receipt of additional funding for longer-term follow-up, and may not be collected for all participants. These participants will continue with standard-of-care NHS follow-up beyond the time duration of the study. Any patients with less than 3 years 'on study' follow up will continue to receive necessary PSA tests, MRI and other imaging, and prostate biopsy as necessary, and/or any additional investigations or treatment, in NHS standard of care pathways beyond the timescale of this study.

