18.2 Definition of Serious Adverse Events

A serious adverse event (SAE) is any untoward medical occurrence that:

- Results in death
- Is life-threatening
- Requires inpatient hospitalisation or prolongation of existing hospitalisation
- Results in persistent or significant disability/incapacity
- Consists of a congenital anomaly or birth defect
- Is otherwise considered medically significant by the Investigator

PART_Protocol_V3.0_15May2024_Clean.docx Page **51** of **77**

Significant medical events are medical events that may jeopardise the participant and may require an intervention to prevent one of the outcomes listed above.

NOTE: The term "life-threatening" in the definition of "serious" refers to an event in which the participant was at risk of death at the time of the event; it does not refer to an event which hypothetically might have caused death if it were more severe.

Seriousness vs severity

A distinction is drawn between serious and severe AEs. Severity is a measure of intensity whereas seriousness is defined using the criteria above. Hence, a severe AE need not necessarily be serious.

18.3 Reporting of Serious Adverse Events (SAEs) from sites to the central study team

Only serious adverse events considered by the site investigator to be related (possibly, probably or definitely) to any of the study procedures and in the opinion of the Principal Investigator are considered unexpected for the study procedure will be collected in the study. Such events must be reported within 24 hours to the central study team using the SAE form within the REDCap study database. Refer to section 18.6 regarding expectedness assessment.

Treatment complications listed in section 18.4 should not be reported on a SAE form unless the complication is (in the opinion of the site investigator) considered more severe in nature than might be expected, or unexpected, for the particular intervention received. For participants undergoing IRE or HIFU treatment, the user manual for the devices should also be referred to when making an assessment of expectedness.

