18.4 Treatment complications

The following treatment-related complications will be collected on the 'Treatment Complications' case report form and should not be reported separately on a SAE form unless the complication is (in the opinion of the site investigator) considered **more severe in nature than might be expected, or unexpected, for the particular intervention** received by the participant:

Events occurring intraoperatively, during the immediate post-operative period, or in the first 31 days post-procedure:

- Thromboembolic disease (DVT/PE)
- Respiratory complications
- Myocardial infarction
- Cerebrovascular accident
- Urine leak post-procedure requiring intervention
- Significant blood loss requiring intervention with either >3 units blood transfusion or packing of the pelvis and/or other surgical/radiological intervention
- Rectal perforation
- Bowel injury

Events occurring at any time during follow-up period likely related to a study intervention:

- Development of a recto-urethral fistula
- Development of a urethro-cutaneous fistula

PART_Protocol_V3.0_15May2024_Clean.docx Page **52** of **77**

- Development of post-procedure urethral stricture disease requiring subsequent surgical intervention
- Development of osteomyelitis
- Ureteric injury

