18.6 Assessment of SAEs by the Principal Investigator (or delegate)

The Principal Investigator (or delegated individual) is responsible for assessing all reported serious adverse events for reason for seriousness, causality and expectedness.

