18.6.2 Expectedness

The Principal Investigator (or delegated individual) is responsible for assessing all serious adverse events for reason for causality. Only serious adverse events considered by the site investigator to be related (possibly, probably or definitely) to any of the study procedures should be reported to the CI or nominated person (NP) in the CTU. Such events must be reported within 24 hours to the central study team using the SAE form within the REDCap study database.

Assessment of expectedness will be made by the CI or NP. An unexpected event is not expected for the study intervention and is not listed in the treatment complications below. If in doubt, the CI will raise queries with the treating medical practitioner.

Related SAEs, which are in the opinion of the nominated person are considered unexpected for the study procedure will be submitted to the REC within 15 days of the CI/CTU becoming aware of the event, using the HRA report of serious adverse event form.

All intervention/study procedure-related SAEs will be recorded and reported to the REC as part of the annual reports.

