18.7 Assessment of SAEs by the Chief Investigator

The CI shall be informed immediately of any SAEs via an automatic database alerting both to the SAE report. The CI shall assess the information in conjunction with any treating medical practitioners and confirm causality and expectedness. If in doubt, the CI will raise queries with the treating medical practitioner.

All intervention/study procedure-related SAEs will be recorded and reported to the REC as part of the annual reports. Unexpected SAEs related to the intervention/study procedures will be reported within the timeframes to the REC as stated below.

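### Protocol 18.3 and 9.2 collect only unexpected related SAEs, while 18.6.2 and 18.7 require all related SAEs, so some expected events can be lost from secondary outcome 3

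*Protocol*

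**What the plan says.** Two collection rules stand in the current text (V3.0).

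- **Related and unexpected only.** 18.3 restricts SAE collection to events that are related and that "in the opinion of the Principal Investigator are considered unexpected for the study procedure will be collected in the study". 9.2 agrees: "Treatment complications and unexpected serious adverse events related to the study intervention will be collected".
- **All related.** 18.6.2 says that SAEs judged "related (possibly, probably or definitely) to any of the study procedures should be reported to the CI or nominated person (NP) in the CTU", within 24 hours and on the REDCap SAE form, with no expectedness condition. 18.7 adds: "All intervention/study procedure-related SAEs will be recorded and reported to the REC as part of the annual reports". The same commitment appears at the end of 18.6.2.

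The assessor of expectedness also differs. In 18.3 it is the Principal Investigator (PI), before anything is sent. In 18.6 the PI or delegate "is responsible for assessing all reported serious adverse events for reason for seriousness, causality and expectedness". In 18.6.2, "Assessment of expectedness will be made by the CI or NP", and 18.7 has the CI confirm it.

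The other stated route for safety events is the Treatment Complications form in 18.4, a named list in two parts. The first is limited to "Events occurring intraoperatively, during the immediate post-operative period, or in the first 31 days post-procedure"; the second is open throughout follow-up. Listed complications go on an SAE form only if unexpected or more severe than expected.

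Secondary outcome 3 (8.3) is "Short, medium and long-term serious adverse events related to treatments", evaluated at 31 days and at 3 years.

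**The concern.** Expectedness normally decides how fast an event is reported onward. In 18.3 it decides whether the event is collected at all. A related SAE that the PI regards as expected, and that has no open item in 18.4, would be left out by a site working from 18.3 and sent in by a site working from 18.6.2.

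Outcome 3 has no expectedness condition, so its count would depend on which section a site follows and on the judgement of an unblinded investigator. The annual REC report and the DSMC, whose remit in 22.4.2 covers all safety aspects, would have the same gap. Reduced side effects are part of the trial's aim (8.1), so a complete count of treatment-related SAEs matters to the interpretation. An analysis plan cannot restore events that were never collected.

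**Working it through.** There is no planned figure to reproduce. The check is to follow each kind of related SAE through the two rules.

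| Related SAE | Under 18.3 and 9.2 | Under 18.6.2 and 18.7 |
|---|---|---|
| Unexpected | SAE form | SAE form |
| Expected, with an open item in 18.4 | Complications form | Complications form |
| Expected, with no open item in 18.4 | Neither form | SAE form |

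Only the third row differs: such an event is recorded 0 times under one rule and once under the other.

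**Can the third row occur?** Yes. 18.6.2 defines an unexpected event by two conditions, not expected for the intervention and not on the complications list, so the two are not treated as the same thing. 18.3 also names the device user manuals as a source of expectedness for IRE and HIFU. An event can therefore be expected without being listed.

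**What 18.4 covers.** The peri-procedural list has 8 items and the any-time list has 5, so 8 + 5 = 13. After day 31 only the 5 remain open, and the only rectal item among them is recto-urethral fistula. Taking 3 years as 3 × 365 = 1,095 days, the period after day 31 is 1,095 − 31 = 1,064 days, and 1,064 / 1,095 = 97% of the window. This shows where the gap lies. It is a share of calendar time, not of events.

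**Two examples**, each depending on the PI judging the event expected:

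1. A serious bowel or rectal injury after day 31, other than recto-urethral fistula. Rectal perforation and bowel injury appear only on the 31-day list, while 7.1 and 7.3 name bowel toxicity as a known effect of radiotherapy.
2. A hospital admission for urinary infection after partial ablation. Admission makes it serious under 18.2. Antibiotic prophylaxis in 13.1.2 and 13.1.3 suggests that infection is foreseen, and 18.4 has no urinary infection or sepsis item.

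**Does the cross-reference settle it?** 18.3 sends the reader to 18.6 for expectedness. 18.6 gives the task to the PI and 18.6.2 gives it to the CI or nominated person, so the reader returns without a single rule.

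**The case against.** The strongest reply is that the gap is narrow. The only events the protocol itself classes as expected are those in 18.4, which have their own form. A PI who used that list as the sole reference would call any unlisted related SAE unexpected and report it even under 18.3. The two examples rest on inference, since the protocol does not label either event expected. On the assessor, 18.7 and 18.8 can be read as site assessment followed by central confirmation. There are other routes too: 16.6 collects treatment complications from treatment start to 36 months and lists SAEs as ad hoc data without an expectedness qualifier, and 9.2 adds notes review, Health Care Use Questionnaires and asking patients.

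Part of this stands. The loss depends on PI judgement, its size is unknown, and the 97% says nothing about risk. The complications form is not shown, and a free field for other events would close part of the gap.

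The conflict remains. The restriction in 18.3 is explicit, and neither the unqualified entry in 16.6 nor 18.8 overrides it. The manuals and the two-part definition allow an unlisted event to be expected. The reviews named in 9.2 are introduced there as means of finding complications and unexpected events. EPIC and the Health Care Use Questionnaire record function and hospital use; they do not give a count of related SAEs.

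**Conclusion.** The point holds. The protocol states two incompatible rules for which SAEs are collected and names different assessors of expectedness. The consequence is confined to related, expected SAEs with no open item in 18.4; unexpected SAEs and the 13 listed complications, within their windows, are captured under either rule. Confidence in the contradiction is high. How many events would be lost, and whether the loss would favour one arm, cannot be derived from the protocol. The conclusion about lost data assumes that some sites follow 18.3, that some PIs judge unlisted events expected, and that the complications form has no free field that catches them. The co-primary endpoints are untouched. It should be corrected because it affects a stated safety comparison and cannot be repaired at analysis.

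**What to change.** Amend 18.3 and 9.2 to the rule already in 18.6.2 and 18.7:

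- Sites report within 24 hours every related SAE not already captured on the Treatment Complications form, whether or not it is expected. The existing exception for listed complications that are unexpected or unusually severe stays.
- The CI or nominated person judges expectedness, and 18.6 is aligned with this. Expectedness then decides only expedited REC reporting.
- The protocol states that outcome 3 counts serious events from both forms.
- For men already treated, sites check once the notes and Health Care Use Questionnaires that 9.2 already has them review, and enter any related SAE held back as expected.

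The 18.4 list can stay as it is. Adding serious rectal or bowel injury to the any-time part, for both arms, is optional.

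The cost is a protocol amendment with REC and local approvals (24.5), a site briefing, some additional SAE forms and more expectedness assessments for the CI or nominated person. The number of extra forms cannot be derived from the protocol. The look-back is one notes check per man treated before the amendment; the protocol does not give that number, and acting early keeps it small. No visit or test is added, and the SAE form already exists in REDCap.

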18.4 Treatment complications

The following treatment-related complications will be collected on the 'Treatment Complications' case report form and should not be reported separately on a SAE form unless the complication is (in the opinion of the site investigator) considered **more severe in nature than might be expected, or unexpected, for the particular intervention** received by the participant:

Events occurring intraoperatively, during the immediate post-operative period, or in the first 31 days post-procedure:

- Thromboembolic disease (DVT/PE)
- Respiratory complications
- Myocardial infarction
- Cerebrovascular accident
- Urine leak post-procedure requiring intervention
- Significant blood loss requiring intervention with either >3 units blood transfusion or packing of the pelvis and/or other surgical/radiological intervention
- Rectal perforation
- Bowel injury

Events occurring at any time during follow-up period likely related to a study intervention:

- Development of a recto-urethral fistula
- Development of a urethro-cutaneous fistula

PART_Protocol_V3.0_15May2024_Clean.docx Page **52** of **77**

- Development of post-procedure urethral stricture disease requiring subsequent surgical intervention
- Development of osteomyelitis
- Ureteric injury

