16.4 Additional treatment/treatment failure

Partial Ablation Arm

Where a positive biopsy result is returned for intermediate-risk PCa during the study follow-up period, either in the previously treated area or in a previously untreated area (demonstrating new intermediate-risk disease), participants will be offered ONE repeat PA treatment of the positive biopsy area.

Primary treatment failure following PA will be determined by repeat prostate biopsies – per protocol or "for cause" or clinical appearance of symptoms/signs/imaging demonstrating disease progression, or due to clinical concern. Biopsies will result in one of four pre-defined scenarios:

- Scenario 1: Negative biopsies, in which case the patient will continue to be followed-up as described.
- Scenario 2: Positive biopsies in a previously untreated or treated area of the prostate demonstrating low-risk low-volume disease, in which case the patient will not require additional treatment and follow-up will continue.
- **Scenario 3:** Positive biopsy for intermediate-risk PCa in the previously treated area, in which case the patient will be offered one repeat PA treatment of the positive biopsy area.
- **Scenario 4:** Positive biopsy for intermediate-risk PCa in a previously untreated area, demonstrating new intermediate-risk disease, in which case the patient will be offered one repeat PA treatment.

Refer to the flow chart below.

Radical treatment arm

For participants in the radical treatment arm receiving RP additional treatment, options will be discussed with the participant, as per standard NHS care. This is usually salvage radiotherapy post-RP with or without androgen deprivation therapy, or androgen deprivation alone. Salvage RP or androgen deprivation will usually be offered where appropriate if post-RRT or LDR-B treatment failure occurs, as per NHS standard care. Refer to flow charts below.

Management of primary treatment failure

Where treatment failure is diagnosed, the patient will be re-staged as appropriate with cross-sectional imaging, and additional appropriate treatment options will be discussed with the participant, as per standard NHS care. For participants in the PA arm these may include salvage RP, external beam RT, or long-term androgen-targeted therapy +/- chemotherapy. For patients in the radical therapy arm this may include an appropriate salvage therapy, or long-term androgen-targeted therapy +/- chemotherapy.

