of men undergoing radical treatment will demonstrate treatment failure. It is hypothesised that radical treatment may be superior to PA in terms of oncological efficacy, but that radical treatment is considerably inferior to PA in terms of functional outcomes. The anticipated worse HRQoL with radical treatment compared with PA, in particular functional outcomes such as urinary continence, erectile function, and bowel toxicity, leads us to consider that radical treatment would need to achieve a 10% lower primary treatment failure rate (e.g. 10% compared to 20%) for it to remain the preferable option in clinical practice. This study is therefore a superiority trial, with treatment failure, and HRQoL and functional outcomes, hypothesised to be superior for PA versus radical treatment. Allowing for a 10% total dropout rate across the entire study, 800 patients randomised on a 1:1 basis to radical treatment or PA would provide approximately 88% power at p < 0.025 to detect a $\geq 10\%$ lower treatment failure rate (10% versus 20%, a hazard ratio of $0.4722 = \log(0.9)/\log(0.8)$) with radical treatment compared to PA treatment. The statistical power would not be much affected if the failure rate in the radical treatment group was somewhat lower, or somewhat higher, than 15%. For example, 800 patients (with 10% dropout) would provide approximately 79% power at p<0.025 to detect a difference of 15% versus 25% in failure rates (hazard ratio 0.5649 = log(0.85)/log(0.75)) and over 95% power to detect a 5% versus 15% failure rate (hazard ratio 0.3156 = log(0.95)/log(0.85)). With 800 patients randomised (and 10% lost to follow-up in total across the study), numerous sample size calculations using various parameters indicate that there will be ample statistical power to detect any meaningful differences in HRQoL scores, e.g. over 90% power at p<0.01 to detect a small to moderate (0.3sd) effect size. Put in perspective, this is a considerably smaller effect size than the 0.5sd effect size described by Norman et al (37) as the minimally important difference for HRQoL differences.

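### Harm collection is worded around the study intervention, so serious late complications of salvage treatment may be missed or unevenly collected, tilting the serious-event comparison towards PA

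*Protocol*

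**What the plan says.** **The outcome.** Protocol section 8.3, objective 3, compares "Short, medium and long-term serious adverse events related to treatments" between arms, with 31 days as short term and 3 years as medium term.

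**Serious adverse events.** Section 18.3 collects "Only serious adverse events considered by the site investigator to be related (possibly, probably or definitely) to any of the study procedures", and only if they are also judged unexpected. Sections 18.6.1 and 18.6.2 judge relatedness and expectedness against the study intervention.

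**Complications.** Section 18.4 has two lists, recorded on the Treatment Complications form.
- Eight events, including rectal perforation and bowel injury, under "Events occurring intraoperatively, during the immediate post-operative period, or in the first 31 days post-procedure".
- Five events (two kinds of fistula, urethral stricture needing surgery, osteomyelitis, ureteric injury) under "Events occurring at any time during follow-up period likely related to a study intervention".

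Section 9.2 also ties the collection of complications and unexpected serious events to the study intervention.

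**Treatment after failure.** Section 16.4 says "additional appropriate treatment options will be discussed with the participant, as per standard NHS care". It continues: "For participants in the PA arm these may include salvage RP, external beam RT, or long-term androgen-targeted therapy +/- chemotherapy". Details of further treatment go on the case report form; complications of that treatment are not mentioned.

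**The concern.** The outcome is worded around treatments in general, while the rules that supply its data are worded around study procedures and the study intervention. An outcome cannot count events that the sites are not asked to report.

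The wording is the same in both arms, but its effect need not be. Salvage follows from failure, and failure depends on allocation. A urethral stricture after allocated prostatectomy is plainly collected. The same stricture after salvage prostatectomy following failed PA is collected only if the site regards the salvage operation as a study intervention. If it does not, a man who has had two courses of treatment contributes the late serious harms of only the first.

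At stake is the comparison of serious events and complications, mainly at the 3-year horizon. That comparison is part of the trade-off between failure and harm which the trial is designed to weigh.

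**Working it through.** **1. Does the text include salvage?** Protocol wording, side by side:

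| Section | Wording used | Does it reach salvage? |
|---|---|---|
| 8.3, objective 3 | related to treatments | Yes, on its face |
| 18.3 | study procedures | Not defined |
| 18.4, first list (8 events) | post-procedure, no further qualifier | Could do |
| 18.4, second list (5 events) | a study intervention | Not defined |
| 9.2 | the study intervention | Not defined |
| 11.1 | study intervention, used for treatment planned under the allocation | Points to no |
| 16.4 | standard NHS care; details of further treatment recorded | Complications not mentioned |
| 16.6 | treatment complications at visits from 3 to 36 months | No restriction stated; the 24- and 36-month lists name failure and repeat PA, not salvage |

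No sentence excludes salvage harms. Usage in 11.1 and 16.4 makes exclusion the natural reading for serious adverse events and the five late complications. The eight early complications are not restricted in this way.

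**2. Which arm loses more?** The sizing hazard ratio reproduces: log(0.9)/log(0.8) = 0.4722, as section 19.2 states. With 800 patients randomised 1:1 and 10% dropout, 360 per arm remain. Failures = 360 × rate:

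| Scenario (PA v radical) | PA | Radical | Excess in PA |
|---|---|---|---|
| 20% v 10% | 72 | 36 | 36 |
| 25% v 15% | 90 | 54 | 36 |
| 15% v 5% | 54 | 18 | 36 |

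The direction is the same in all three. The ratio is not: 2.0, 1.67 and 3.0.

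**3. What share of events could come from salvage?** Let f be the failure rate, u the proportion of failures given salvage, r the repeat-PA rate, and let every treatment course carry the same risk of a serious event. The documents do not give u, r or the risk, so these are assumptions.

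- PA share = fu / (1 + r + fu)
- Radical share = fu / (1 + fu)

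With f = 0.20 (PA) and 0.10 (radical), and r from 0 to 0.3:

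- u = 1: PA 0.20/1.20 = 16.7% to 0.20/1.50 = 13.3%; radical 0.10/1.10 = 9.1%.
- u = 0.5: PA 0.10/1.10 = 9.1% to 0.10/1.40 = 7.1%; radical 0.05/1.05 = 4.8%.

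So about 7-17% of PA-arm and 5-9% of radical-arm treatment-related events would arise from salvage. If a salvage course carried twice the risk, at full uptake, the shares would be 0.40/1.40 = 28.6% to 0.40/1.70 = 23.5% for PA, and 0.20/1.20 = 16.7% for radical.

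**4. What difference between arms could go uncounted?** Each scenario has a 10-point gap in failure. Missed difference = 0.10 × uptake × risk of serious harm per salvage course. Assuming uptake of 50-100% and risk of 5-30%:

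- low: 0.10 × 0.5 × 0.05 = 0.25 percentage points
- high: 0.10 × 1.0 × 0.30 = 3.0 percentage points

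The shares in step 3 and the difference in step 4 are upper limits under their assumptions, because events caught by the 31-day list would not be lost.

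**The case against.** The strongest reply is that this is ambiguity, not exclusion. The 31-day list is not limited to the allocated procedure, so a rectal perforation at salvage prostatectomy can be recorded as the text stands. Safety reporting runs to each man's final follow-up (18.1). Prostatectomy and radiotherapy are trial treatments, so a site could call salvage prostatectomy a study intervention. The label of standard NHS care does not settle it, since the allocated radical treatments are usual care too. All of this stands, and it limits the gap to serious adverse events and the five late complications. It does not close the gap: if the terms can be read either way, sites will differ.

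Three stronger readings are tempting, and the documents do not support them.

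- *The sizing expects salvage twice as often after PA.* Section 19.2 gives 10% against 20% as an example of what radical treatment would have to achieve to remain preferable. It concerns failure, which in the radical arm includes PSA-only criteria. No salvage rate is given. The same section also contains a sentence hypothesising that failure is better with PA, at odds with its own scenarios.
- *The whole harm comparison is biased.* PORPUS-P, EPIC and IPSS continue in both arms to the end of the study and are analysed by intention to treat, so functional harm after salvage is kept. Resource-use data also cover further interventions and side effects, though for costing and not as outcome 3.
- *The intention-to-treat rule is broken.* Section 19.5 fixes the arm in which a man is analysed, not which events are ascertained.

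Nor is the PA share above 10% in every case: at 50% uptake it is 7-9%. With a minimum follow-up of 12 months and the first protocol biopsy 12 months after treatment, some salvage will also fall after the study closes.

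**Conclusion.** The point holds in a limited form. The data rules for serious adverse events and late complications are narrower than the outcome they serve, and the terms that set their scope are undefined. Read naturally, they drop serious late harms of salvage; read variously, they collect them unevenly. Either way the loss is larger in the arm with more failures. That is PA under every scenario used for sizing, and it would reverse if radical treatment failed more often.

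The size is uncertain but not negligible: 7-17% of PA-arm against 5-9% of radical-arm treatment-related events would come from salvage, on the 20% v 10% scenario with equal risk per course, 50-100% uptake and 0-30% repeat PA. Only the part outside the 31-day list would be lost. The PORPUS-P comparison is not affected. The correction is worth making because it is cheap and removes a directional bias from a stated between-arm comparison.

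**What to change.** - In 18.4, and in the matching sentence of 9.2, state that the listed complications are recorded on the Treatment Complications form in both arms after any prostate cancer treatment received after randomisation, whether allocated, repeat or salvage.
- Confirm that the 31-day list applies after each such procedure.
- Add one field to the form naming the treatment judged to have caused the event.
- Analyse outcome 3 as randomised over all such treatments, with events from first-line treatment alone as a supporting table.

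Expedited reporting of serious adverse events in 18.3 and to the ethics committee in 18.8 need not be widened. Extending 24-hour and 15-day reporting to all later care, including long-term systemic therapy, would add burden that the outcome does not need.

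Cost: a protocol wording change, one form field and slightly more site reporting. Further treatment is already recorded under 16.4, so no visits are added and no clinical rule changes.
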